# **Overall strategy**

#### Overview

The overarching goal of this small exploratory open-label pilot study is to explore [C]butyrate PET and [F]FDG PET glucose metabolism and clinical measures before and after open-label treatment with the SCFA prodrug tributyrin in a small pilot study in PD (n=8) and normal control older adults (n=2). Positive findings in this small exploratory pilot trial may support target engagement study of SCFA supplementation in normal adults and PD. PET and/or MRI Imaging protocols will be optional for a separate subset of 10 participants may also complete the study based on clinical or laboratory test battery alone for the exploratory hypothesis.

Timetable: This study, to be conducted over a 2-year period, will include a net total of n=20 subjects (NC, n=4; PD, n=16; total net; n=20; gross n=32 to allow for attrition). Details of the enrollment and major test procedures are listed in **table 1** below.

*Milestone* of recruitment success are net completion of 9 persons for year 1.

Table 1: Study enrollment & main       assessments	NC	PD	TOTAL
Baseline [  C]butyrate PET and [  F]FDG PET-CT & brain MRI with baseline clinical assessment	NC=2	PD=8	n=10
Post-intervention [  C]butyrate PET and [  F]FDG PET-CT & MRI	NC=2	PD=8	n=10
30-day (± 7) tributyrin intervention with pre/post clinical assessments)	NC=4	PD=16	n=20
Exploratory clinical and laboratory test battery pre and post the tributyrin supplement intervention	NC=4	PD=16	N=20
Total subject net recruitment aims 1 & 2	NC=4	PD=16	n=20*

Design: Exploratory open-label tributyrin supplementation pilot study.

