There will be a total of 5 visits for this pilot study. The first two visits will consist of the initial general clinical assessment (e.g., vital signs, vital capacity lung/breath holding tests) and optional imaging split over 2 days (no specific sequence or preset time interval). At visit 1 participants will be instructed to wear physical activity and sleep trackers (called ActivPal a sensor will be put on the upper leg and a ring called Oura ring, which will be worn at a finger) for 1 week prior to visit 2. Participants will also wear a continuous glucose monitor during the same time. After the participants complete the 1 week of physical activity, sleep and glucose monitoring they will return for visit 3, where a limited repeat clinical test battery will be administered. At visit 3 the participant will also be instructed to start the approximately 30 day supplementation of tributyrin. The physical activity and sleep trackers and the continuous glucose monitor will also be worn during the last week of the tributyrin supplementation period. At the end of the approximately 30-day tributyrin supplementation the participants will return for visits 4 (repeat clinical assessment) and 5 (repeat optional imaging) again split over 2 days. There is no pre-set sequence which assessment (clinical or imaging) comes first. Blood and/or saliva tests will be collected for assessments of genetic variables (e.g. ApoE). Blood assessment will also be used for metabolomics. Blood continuous glucose data will be collected blinded to the participant.

Table 2 Schedule of activities	Visit 1* / Visit 2*: Baseline assessm ent (clinical)	Visit 1* / Visit 2* Baseline assessment (imaging – OPTIONAL)	At-home wearable sensor use (1 week ± 3 days)	Visit 3 Pre- intervention assessment	At-home 4 (± 1) week Tributyrin (500 mg tid po) intervention	Visit 4* / Visit 5* Post- intervention clinical assessment (while on tributyrin)	Visit 4* / Visit 5* Post- intervention imaging assessment (while on tributyrin, OPTIONAL)
Approximate time commitment	4-6 hours	3-6 hours	-	4-5 hours	-	4-6 hours	3- 6 hours
Test location	Domino s Farms	UM hospital	Home	Dominos Farms	Home	Dominos Farms	UM hospital
Informed Consent (or prior eConsent)	Х						
Eligibility	Х						

Details for the schedule of activities for the tributyrin supplement intervention study are shown below (Table 2).

OPTIONAL		Х					X (after
[  C]butyrate,		~					taking
[  F]FDG							tributyrin)

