PET-CT 1.2							(induty)
(brain/body)*							
		Х					V
In case of		X					Х
[  C]butyrate PET,							
obtain vital signs							
pre- & post							
injection of tracer							
OPTIONAL MRI		Х					X
brain*							
DEXA Bone	Х					Х	
Density Scan							
Blood/saliva/urine	Х					Х	
sample collection 							
Continuous			Х		X (last 7	Х	
glucose monitor					days)		
for 7±3 days					- /		
Sleep tracking ring			Х	Х	Х	Х	
139					-		
Activity tracker for			Х		X (last 7		
7±3 days					days)		
Motor MDS	Х			Х	j /	Х	
UPDRS 	~			X		Λ	
Balance test	Х			Х		Х	
MiniBESTest	^			~		~	
(sensored) 	V			V		Х	
Pegboard testing 	X X			X X		 	
Foot Tapping 			-				
Finger Tapping 	Х			Х		Х	
Electronic Gait	Х			Х		Х	
Mat/sensored							
walk 			_				
Beck Depression	Х			Х		Х	
Inventory II scale							
Spielberger Trait	Х			Х		Х	
Anxiety Scale							
Sleepiness scales	Х					Х	
MoCa,	X X			X (optional)		X X	
PDCRS (limited							
cognition)							
Cognitive test	Х			X (optional)		Х	
battery							
PCFRS functional	Х			1		Х	
scale	~					~	
Quality of life	Х					Х	
scale PDQ-39	^					~	
Adverse event	Х		+	Х		Х	
	^			^		^	
assessment					Х		
Phone Call/Email					X		
Drug monitoring							
Drug				Х		Х	X
accountability							
Pregnancy test in		Х	1	Х			Х
women of							

childbearing	(within 48		(within 48
potential	hours of		hours of
	PET)		PET)

Note

: Fasting in morning

: Dopaminergic off state in PD

\*Visits 1-2 and 4-5. There is no pre-set sequence which assessment (clinical or imaging) comes first.

Details of the neuropsychological test battery is shown in Table 3.

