A urine pregnancy test will be performed on all women of childbearing potential within 48 hours prior to the PET scanning session, and urine sampling may be performed on subjects at baseline and post-interventions as an additional screening measure.

Risks associated with tributryin: The risks to participants are very minimal. Although tributyrin is taken for symptoms of irritable or inflammatory bowel disease it is possible that nausea or indigestion may occur. However, these gastrointestinal side effects are both rare and mild. Tributyrin is received GRAS (Generally Regarded As Safe) certification from the FDA, is commercially available in the United States and prior work has shown that the dosing regimen proposed in this study has been found to be safe and generally well-tolerated.

**Data Study Monitoring Plan (DSMP):** Drs. [name] and [name] will act as the Data Safety Monitoring Plan members for this study. All adverse events and other study related events will be discussed at monthly investigator meetings. Study team will document any adverse events specifically related to study participation (imaging, clinical visit, at-home supplement and/or device usage, etc.). Adverse events will be classified according to standard criteria and reported to the IRBMED (relevant University of Michigan IRB) according to standard guidelines. Serious adverse events will be reported within 24 hours.

For risk of suicidality (if participants select answer responses 2 or 3 for question 9 on the Beck Depression Inventor, i.e. 'I would like to kill myself' (answer 2) or 'I would like to kill myself if I had a chance' (answer 3) then the staff will hand out the UM Depression brochure, refer to the contact information and also inform [name] or [name] who will discuss this with the participant. The face to face conversation with the physicians must occur during that visit and must not be deferred. There must be a safety plan in place before the patient can leave the building.

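### The only sentence on documenting adverse events is limited to participation-related events, and Table 2 appears to schedule no adverse-event check at the on-drug imaging visit

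*Combined protocol and SAP*

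**What the plan says.** The DSMP paragraph, under Potential Risks, makes four statements in sequence about adverse events.

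- Discussion: "All adverse events and other study related events will be discussed at monthly investigator meetings".
- Documentation: "Study team will document any adverse events specifically related to study participation (imaging, clinical visit, at-home supplement and/or device usage, etc".
- Classification and reporting: adverse events are to be classified by standard criteria and reported to the IRB under standard guidelines. Neither the criteria nor the guidelines are set out in the document.
- Serious events: "Serious adverse events will be reported within 24 hours".

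Table 2 (Schedule of activities) has a row for adverse-event assessment. Legible marks stand under the baseline clinical visit, Visit 3 and the post-intervention clinical visit. The last column is headed, in part, "intervention imaging assessment (while on tributyrin, OPTIONAL". It carries a drug-accountability mark, but no adverse-event mark can be seen there.

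On timing, the Methods text says that participants "return for visits 4 (repeat clinical assessment) and 5 (repeat optional imaging) again split over 2 days". The note to Table 2 adds: "There is no pre-set sequence which assessment (clinical or imaging) comes first".

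**The concern.** There are two separate matters.

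The first is the order of judgement. If only events considered related are written down, someone decides on relatedness before there is a record. The study has one arm and is open-label, so there is no comparator to help with that decision. The effects named for tributyrin, nausea and indigestion, are non-specific, and a single case is easily put down to something else. If such a case is not recorded, it cannot be reconsidered when the same complaint appears in another participant.

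The second is the schedule. A participant whose imaging comes after the post-intervention clinical visit is still taking tributyrin and receives tracer injections that day. On the visible marks, nobody is scheduled to ask that participant about adverse events at that visit or later.

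**Working it through.** The plan gives no figure on this point to reproduce. The check is a comparison of sentences, a reading of one table row, and a count.

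**1. Scope of each DSMP provision**

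| Action | Events covered | Relatedness limit |
|---|---|---|
| Monthly discussion | All adverse events | None |
| Documentation | Those related to participation | Yes |
| Classification and IRB reporting | Adverse events | None |
| 24-hour reporting | Serious adverse events | None |

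One provision of four is limited, and it is the one about recording. Its bracket names sources of related events (scans, visits, supplement, devices). That brings events at the scan into scope, but it does not bring in events presumed unrelated. What the literal wording leaves open is therefore mainly the non-serious event presumed unrelated.

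**2. The adverse-event row of Table 2**

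In the machine-read text the table is broken, so alignment was checked against a neighbouring row.

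- Adverse-event row: marks align with baseline clinical, Visit 3 and post-intervention clinical.
- Drug-accountability row: marks align with Visit 3, post-intervention clinical and post-intervention imaging. The last column therefore survives in this part of the table.
- The continuation line of the adverse-event row carries a further X, aligned with the at-home tributyrin column. It may belong to this row, or it may duplicate the phone/email mark on the next line. The text cannot settle which. In either case it is not in the imaging column.

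**3. Which imaging visit is exposed**

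- Baseline imaging is followed by Visit 3: after the week of monitoring "they will return for visit 3, where a limited repeat clinical test battery will be administered". Visit 3 has an adverse-event mark, so baseline imaging is covered.
- Post-intervention imaging is covered if the clinical visit follows it. If imaging comes last, no marked check follows.

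**4. How many participants**

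The inputs are planned net numbers. The Overview describes the imaging part as a "small pilot study in PD (n=8) and normal control older adults (n=2"), and Table 1 gives the same split. The Timetable gives a net total of 16 PD and 4 controls.

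- Imaged: 8 + 2 = 10. Total: 16 + 4 = 20.
- Minimum imaged last: 0/20 = 0%.
- Maximum imaged last: 10/20 = 50% (PD 8/16 = 50%; controls 2/4 = 50%).

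The order of Visits 4 and 5 is left open, so there is no basis for a point estimate within that range. The documents also give no basis for a number of unrecorded events under the DSMP wording.

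**The case against.** The strongest reply on the wording is that three of the four DSMP provisions are unrestricted, as is the adverse-event row of Table 2. Asking about an event, discussing it monthly and classifying it all presuppose some record. The documentation sentence does not say 'only', its list is open-ended, and the IRB guidelines it leads to may require more. This stands in part. It is a reasonable account of what the investigators may intend, but the text does not say it, and the one sentence on recording is narrower than the rest.

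On the schedule, several safeguards exist: phone/email drug monitoring and a daily drug diary during dosing, vital signs before and after the butyrate tracer, attending staff, and a physician available at the PET facility. The time between Visits 4 and 5 is not stated and may be very short. All of this reduces the importance of the missing mark. None of these contacts is described as an adverse-event enquiry, however. The vital signs and physician cover concern reactions at the scan, and not what has happened since the clinical visit. The further X discussed above may indicate an at-home enquiry, but nothing ties it to the interval before a final imaging visit.

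A reader might infer that the plan tells staff to discard unrelated events, that serious events could be lost, or that events at the scan go undocumented. The documents support none of these. No sentence orders an exclusion, the 24-hour rule has no relatedness limit, and imaging is named in the documentation sentence. What is missing at the scan is a scheduled prompt.

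**Conclusion.** A minor point that is worth correcting because the correction is cheap. The DSMP sentences do not match. On a literal reading, relatedness is judged before recording, and the effect falls mainly on non-serious events presumed unrelated. Separately, 0 to 10 of 20 planned participants (0% to 50%) could have no scheduled adverse-event check at or after their last on-drug visit.

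The upper figure should not be read as half the participants having missed events. It counts people who could be imaged last and says nothing about how many events would occur or be overlooked.

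The conclusion rests on three assumptions: that the documentation sentence is applied as written, that the planned net numbers hold, and that the blank in the imaging column is in the original Table 2 and was not produced by text extraction. The wording part does not depend on the third. Confidence in the table part is moderate at most until the original is checked.

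**What to change.** Reconcile the DSMP sentences by replacing the documentation sentence with something like: *The study team will document all adverse events reported or observed from the start of participation through the last study visit, regardless of presumed cause, and any later event considered related to participation (for example from scans, visits, the supplement or a device), and will then classify each for relatedness and seriousness.*

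The clause on later events is needed. The present sentence has no end date, so a cut-off at the last visit alone would drop a late participation-related event that it now covers, such as an infection at the puncture site after a final PET visit.

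For Table 2, first confirm the adverse-event row in the original, including which row the further X belongs to. If the imaging column is indeed blank, add an adverse-event mark to the post-intervention imaging column, so that whichever of Visits 4 and 5 comes last has a check.

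The cost is one sentence, one mark and a few minutes at a visit that already takes place. The downside is a longer event log in which many entries will probably be unrelated.
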